10. SUBJECT COMPLETION/DISCONTINUATION OF STUDY VACCINE/ WITHDRAWAL FROM THE STUDY

10.1. Completion

A subject will be considered to have completed study vaccination if he or she has received both vaccinations on Day 1 and the vaccination on Day 29. A subject will be considered to have completed the study if he or she has completed assessments at the final visit 6 months after the second vaccination.

10.2. Discontinuation of Study Vaccine/Withdrawal from the Study

Discontinuation of Study Vaccine

A subject will not be automatically withdrawn from the study if he or she has to discontinue from study vaccination before the end of the study vaccine regimen.

Subjects will be discontinued from study vaccine administration for the reasons listed below. These subjects must not receive any additional dose of study vaccine but should continue other study procedures, eg, safety follow-up:

- Anaphylactic reaction following vaccination, not attributable to causes other than vaccination
- Any related SAE
- Any related AE, worsening of health status or intercurrent illness that, in the opinion of the investigator, requires study vaccine discontinuation

Withdrawal from the Study

Each subject has the right to withdraw from the study at any time for any reason without affecting the right to treatment by the investigator. Although the subject is not obliged to give a reason for withdrawing prematurely, the investigator should make a reasonable effort to ascertain the reason(s) while fully respecting the subject's rights.

A subject will be withdrawn from the study for any of the following reasons:

- Repeated failure to comply with protocol requirements
- Decision by the sponsor or the investigator to stop or cancel the study
- Decision by local regulatory authorities and Institutional Review Board/Independent Ethics Committee (IRB/IEC) to stop or cancel the study
- Lost to follow-up
- Withdrawal of consent
- Death

Any unnecessary study discontinuation should be avoided. Should a subject be withdrawn, all efforts should be made to complete and report the observations as thoroughly as possible. Whenever a subject is withdrawn from the study, independent of the reason, a final evaluation should be completed for that subject and the major reason for which the subject was withdrawn must be stated. If a subject is lost to follow-up, every reasonable effort must be made by the study-site personnel to contact the subject and determine the reason for discontinuation/withdrawal. The measures taken to follow-up must be documented.

When a subject withdraws before completing the study, the reason for withdrawal is to be documented in the eCRF and in the source document. Study vaccine assigned to the withdrawn subject may not be assigned to another subject. In general, subjects who withdraw will not be replaced, unless that subject was randomized but did not receive any study vaccine. However, any randomized subject withdrawn from the study for reasons other than due to an AE after the first dose but before the second dose might be replaced at the discretion of the sponsor.

If a subject withdraws early from the study, assessments for early withdrawal should be obtained (see Section 9.1.8).

Subjects who wish to withdraw consent from participation in the study will be offered a single exit visit for safety follow-up (prior to formal withdrawal of consent). They have the right to refuse.

Withdrawal from the Use of Samples in Future Research

The subject may withdraw consent for use of samples for future research (refer to Section 16.2.5). In such a case, samples will be destroyed after they are no longer needed for the clinical study. Details of the sample retention for research are presented in the main ICF.

10.3. Contraindications to Vaccination

The following events constitute a contraindication to vaccination at that point in time. If any of these events occur at the scheduled time for vaccination, the subject may be vaccinated up to 10 days beyond the scheduled vaccination, or be withdrawn from further vaccination at the discretion of the investigator and after consultation with the sponsor:

- Severe acute illness at the time of vaccination. This does not include minor illnesses such as diarrhea.
- Fever (body temperature ≥ 38.0 °C) at the time of vaccination.

Note: Other licensed vaccines should be given at least 14 days before or 14 days after study vaccine administration (see Section 4.3).

11. STATISTICAL METHODS

Statistical analysis will be done by the sponsor or under the authority of the sponsor. A general description of the statistical methods to be used to analyze the immunogenicity and safety data is outlined below. Specific details will be provided in the Statistical Analysis Plan (SAP).

Planned analyses are described in Section 11.6.

The vaccine groups are labeled “CoAd” and “Control” as follows in the remainder of this section:

Group	N	Day 1	Day 29
CoAd	90	Ad26.RSV.preF (1×10^{11} vp) + Fluarix	Placebo
Control	90	Placebo + Fluarix	Ad26.RSV.preF (1×10^{11} vp)

11.1. Analysis Sets

The Full Analysis (FA) Set includes all subjects who were randomized and received at least one dose of study vaccine, regardless of the occurrence of protocol deviations and vaccine type

(seasonal influenza, Ad26.RSV.preF or placebo). Vaccination assignment will follow the as-treated principle. All safety and subject information analyses will be based on the FA set.

The Per-protocol Influenza Immunogenicity (PPII) Set will include all subjects who were randomized and received the first vaccination for whom immunogenicity data are available, excluding subject samples with major protocol deviations expecting to impact the immunogenicity outcomes.

In addition, the following samples will not be included in the PPII set:

- For subjects who experience a seasonal influenza infection (based on RT-PCR, or other sources), samples taken after the natural infection will not be taken into account in the assessment of the immunogenicity of the seasonal influenza vaccine

The analysis of primary immunogenicity endpoint will be based on the PPII set. The analysis of all secondary and exploratory immunogenicity endpoints related to influenza will also be based on the PPII set. Depending on the number of samples excluded, a post-hoc exploratory analysis might be performed, including the excluded samples. To visualize these excluded samples, subject profiles from several assays might be repeated, indicating the excluded samples.

The Per-protocol RSV Immunogenicity (PPRI) Set will include all randomized and fully vaccinated subjects (all three vaccinations, ie, seasonal influenza, Ad26.RSV.preF and placebo) for whom immunogenicity data are available, excluding subject samples with major protocol deviations expecting to impact the immunogenicity outcomes.

In addition, the following samples will not be included in the PPRI set:

- For subjects who experience a natural RSV infection (based on RT-PCR, or other sources), samples taken after the natural infection will not be taken into account in the assessment of the immunogenicity of Ad26.RSV.preF

The analysis of all secondary and exploratory immunogenicity endpoints related to RSV will also be based on the PPRI set. Depending on the number of samples excluded, a post-hoc exploratory analysis might be performed, including the excluded samples. To visualize these excluded samples, subject profiles from several assays might be repeated, indicating the excluded samples.

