Nasal turbinate samples will be stored refrigerated at home and brought to the site within the next 3 to 4 days. The presence of RSV infection will be assessed by the sponsor by reverse transcriptase polymerase chain reaction (RT-PCR) diagnostics on the nasal turbinate samples.

Blood from any subject with a suspected RTI may be assayed by a serological assay (eg, protein G and/or N ELISA) to confirm RSV infection. *Note:* No additional blood sampling is necessary – any serological assay conducted to confirm RSV infection will use blood from the existing samples. Signs and symptoms of RTIs will also be reported as unsolicited AEs if they occur between first vaccination and 28 days following the second vaccination; any RTI fulfilling the criteria of an SAE would be reported as such during the entire study period.

SUBJECT POPULATION

Subjects will be adult men and women, aged ≥ 60 years on the day of signing the ICF. All subjects will be in good or stable health (on the basis of physical examination, medical history, 12-lead electrocardiogram (ECG) and vital signs measurement performed on Day 1).

DOSAGE AND ADMINISTRATION

On Day 1 and Day 29, each subject will receive separate intramuscular injections of Ad26.RSV.preF or placebo, and of a seasonal influenza vaccine, according to the schedule shown in [Table 1](#).

- Ad26.RSV.preF (JNJ-64400141): will be supplied at a concentration of 2×10^{11} vp/1.0 mL in single-use vials (0.5 mL extractable volume). A dose level of 1×10^{11} vp will be used
- Fluarix[®] Quadrivalent (suspension for intramuscular injection): 2017/18 season influenza vaccine
- Placebo (saline solution)

For each subject, each injection will be 0.5 mL in volume. On Day 1, subjects will receive two intramuscular injections, one in each arm; on Day 29, subjects will receive one intramuscular injection. The right arm should be used for seasonal influenza vaccination doses on Day 1; the left arm should be used for Ad26.RSV.preF/placebo doses on Days 1 and 29.

An unblinded pharmacist, or other qualified individual, who will have no other study function will prepare the appropriate vials and syringes, labeled with the subject's identification number, and provide the syringes for Ad26.RSV.preF and placebo in a blinded manner to the blinded study vaccine administrator (ie, blinded for Ad26.RSV.preF; Fluarix administration will not be blinded) who will perform the injection.

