- If feasible, subjects should take a nasal turbinate sample at home. Alternatively, subjects may go to the site within 1-2 days of the start of the RTI to have nasal turbinate samples taken by study staff.

Nasal turbinate samples will be stored refrigerated at home and brought to the site within the next 3 to 4 days. The presence of RSV infection will be assessed by the sponsor by reverse transcriptase polymerase chain reaction (RT-PCR) diagnostics on the nasal turbinate samples.

Blood from any subject with a suspected RTI may be assayed by a serological assay (eg, protein G and/or N ELISA) to confirm RSV infection. *Note:* No additional blood sampling is necessary – any serological assay conducted to confirm RSV infection will use blood from the existing samples.

Signs and symptoms of RTIs will also be reported as unsolicited AEs if they occur between first vaccination and 28 days following the second vaccination; any RTI fulfilling the criteria of an SAE would be reported as such during the entire study period. Signs and symptoms of RTIs will be collected on the RTI Symptoms page in the eCRF, and also on the AE page in the eCRF if they occur between first vaccination and 28 days following the second vaccination.

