11.2. Sample Size Determination

Sample size calculations are performed under the following assumptions:

- immune response is measured by HI antibody titers against the four influenza vaccine strains
- a standard deviation of 2 at the \log_2 scale for HI antibody titers.

As four seasonal influenza strains will be assessed for which non-inferiority is to be shown, 94.6% power is required for each individual seasonal influenza strain to ensure an overall power of at least 80%. To have 94.6% power for an individual influenza strain, 86 evaluable subjects/group are required. If approximately 5% subjects are unevaluable (due to dropout, missing data, or seasonal influenza), 90 randomized subjects/arm will be needed.

This sample size ensures at least 80% power, assuming statistical independence between the HI antibody titers for the four seasonal influenza strains. As some correlation between the responses to the four strains is likely, the actual overall power may be higher.

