11.4. Immunogenicity Analyses

The **primary immunogenicity objective** is to demonstrate the non-inferiority of the concomitant administration of Ad26.RSV.preF and seasonal influenza vaccine versus the administration of seasonal influenza vaccine alone in terms of humoral immune response expressed by the GMTs of HI antibody titers against all four influenza vaccine strains 28 days after the administration of influenza vaccine, using a non-inferiority margin of 2 for the GMT ratio (Control group/CoAd group).

The primary immunogenicity objective will be assessed by calculating the 95% one-sided upper confidence limit for the difference in log-transformed HI antibody titers for each of the four seasonal influenza vaccine strains between Control and CoAd groups. The confidence limit will be calculated using Welch's t-interval method. The confidence limit will be back-transformed (by exponentiation) to a GMT ratio and compared to the non-inferiority limit of 2.

Only if the 95% one-sided upper confidence limit for the GMT ratio (Control group/CoAd group) of the HI antibody titers lies below 2 for each of the four vaccine strains, non-inferiority of co-administration versus separate administration will be concluded. If one or more confidence limits for the GMT ratio exceed 2, non-inferiority cannot be concluded.

As a sensitivity analysis, the primary endpoint will also be evaluated adjusting for baseline HI levels.

The **secondary and exploratory efficacy endpoints** are listed in Section [2.1](#).

Continuous secondary and exploratory variables will be summarized with descriptive statistics of the actual values and the changes from baseline where appropriate. Descriptive statistics (geometric mean and 95% confidence interval for ELISA, virus neutralization and HI assays; median and quartiles for ELISpot and intracellular cytokine staining [ICS]) will be calculated for continuous immunologic parameters at all timepoints. For the humoral assays, geometric mean

fold rises from baseline and corresponding 95% confidence intervals might additionally be calculated. For immunogenicity, baseline is considered as the last assessment pre-vaccination. Graphical representations of immunologic parameters will be made as applicable.

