11.6. Planned Analyses

- **28 days post-first dose immunogenicity analysis:** at 28 days post-first dose, an immunogenicity analysis will be performed by an independent unblinded statistician. The goal of this analysis will be to evaluate the non-inferiority of the concomitant administration of Ad26.RSV.preF and seasonal influenza vaccine versus the administration of seasonal influenza vaccine alone in terms of the humoral immune response expressed by the GMTs of HI antibody titers against the four influenza vaccine strains. The independent unblinded statistician and unblinded biomarker representative will present data to the DRC if non-inferiority of concomitant versus separate administration is not demonstrated. The DRC will decide if subjects should be offered repeat influenza immunization after Day 57. If non-inferiority is not demonstrated but the following criteria⁸ are fulfilled, subjects would not be revaccinated:
 - The lower bound of the 95% confidence interval for the percentage of subjects achieving seroconversion for HI antibody should meet or exceed 30%
 - The lower bound of the 95% confidence interval for the percentage of subjects achieving an HI antibody titer $\geq 1:40$ should meet or exceed 60%
- **Primary analysis:** 28 days post-second dose safety and immunogenicity analysis. This analysis will be performed based on unblinded data. The goal of this analysis will be to evaluate the primary objectives. The blind will be maintained at the subject/site level.

- **Final analysis:** 6 months post-second dose safety analysis. This analysis will be performed based on unblinded data. The goal of this analysis will be to assess safety.

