12.1. Definitions

12.1.1. Adverse Event Definitions and Classifications

Adverse Event

An AE is any untoward medical occurrence in a clinical study subject administered a medicinal (investigational or non-investigational) product. An AE does not necessarily have a causal relationship with study vaccine. An AE can therefore be any unfavorable and unintended sign (including an abnormal finding), symptom, or disease temporally associated with the use of a medicinal (investigational or non-investigational) product, whether or not related to that medicinal (investigational or non-investigational) product (Definition per International Conference on Harmonisation [ICH]).

This includes any occurrence that is new in onset or aggravated in severity or frequency from the baseline condition, or abnormal results of diagnostic procedures, including laboratory test abnormalities.

Note: The sponsor collects unsolicited AEs starting from ICF signature for 28 days after the second vaccination, and solicited AEs from the time of each vaccination for 7 days post-vaccination (refer to Section 12.3.1 for time of last AE recording). SAEs will be collected from ICF signature for the duration of the study. RTIs, preferably as a diagnosis, will be reported on the AE page of the eCRF if they occur between first vaccination and 28 days following the second vaccination; any RTI fulfilling the criteria of an SAE would be reported as such during the entire study period.

Serious Adverse Event

An SAE based on ICH and EU Guidelines on Pharmacovigilance for Medicinal Products for Human Use is any untoward medical occurrence that at any dose:

- Results in death
- Is life-threatening
(The subject was at risk of death at the time of the event. It does not refer to an event that hypothetically might have caused death if it were more severe)
- Requires inpatient hospitalization or prolongation of existing hospitalization
- Results in persistent or significant disability/incapacity
- Is a congenital anomaly/birth defect
- Is a suspected transmission of any infectious agent via a medicinal product
- Is Medically Important*

*Medical and scientific judgment should be exercised in deciding whether expedited reporting is also appropriate in other situations, such as important medical events that may not be

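### Does the influenza exclusion from the primary analysis set rest on an RT-PCR test that the study never performs?

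*Protocol*

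**What the plan says.** Protocol Section 11.1 makes the per-protocol influenza immunogenicity (PPII) set the basis of the primary analysis and removes some samples from it: "For subjects who experience a seasonal influenza infection (based on RT-PCR, or other sources), samples taken after the natural infection" are left out of the assessment of the influenza vaccine. Section 11.2 counts such cases in its attrition allowance: "If approximately 5% subjects are unevaluable (due to dropout, missing data, or seasonal influenza), 90 randomized subjects/arm will be needed". Section 11.4 concludes non-inferiority only if the upper limit of the GMT ratio "lies below 2 for each of the four vaccine strains".

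The diagnostic procedures are in Section 9.2.3 and repeated in the synopsis. On sampling: "If feasible, subjects should take a nasal turbinate sample at home", or have it taken at the site. On testing: "The presence of RSV infection will be assessed by the sponsor by reverse transcriptase polymerase chain reaction (RT-PCR) diagnostics on the nasal turbinate samples". Existing blood from a subject with a suspected respiratory infection "may be assayed by a serological assay (eg, protein G and/or N ELISA) to confirm RSV infection". Influenza is not mentioned in these procedures.

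Section 12.1.1 adds a clinical route: "RTIs, preferably as a diagnosis, will be reported on the AE page of the eCRF" from the first vaccination until 28 days after the second.

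**The concern.** The PPII rule and the RSV rule in Section 11.1 share the same wording, with RT-PCR as the first basis for declaring an infection. For RSV, Section 9.2.3 supplies that RT-PCR. For influenza, no section does. The HAI and the exploratory influenza neutralization assay are listed as measures of vaccine response, not as infection diagnostics. The rule that acts on the primary endpoint therefore seems to depend on a result that the described procedures do not produce. Nor is this simply a matter for the SAP: an analysis plan can define other sources, but it cannot create a laboratory result.

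At stake is the HI titer 28 days after vaccination with the 2017/18 influenza vaccine. Influenza between Day 1 and the Visit 3 draw would raise titers, and an undetected case would stay in the primary set. An equal rise in both arms only adds noise. If infected subjects instead reached similar titers whatever their vaccine response, the GMT ratio would move toward 1, which favors a non-inferiority conclusion.

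**Working it through.** **Inputs from the protocol.** Margin 2 for the GMT ratio, that is log2(2) = 1; one-sided 95% limit by Welch's method (11.4); SD 2 on the log2 scale; 86 evaluable per group; 94.6% power per strain; strains treated as independent (11.2). A true ratio of 1 for the power calculation is an assumption, since Section 11.2 states none.

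**The plan's own figure.** SE = 2 × √(2/86) = 0.305. With the noncentral t on 170 degrees of freedom, power is 94.75% per strain (n = 85 gives 94.54%, just short of 94.6%). Overall: 0.9475⁴ = 80.6%. The stated 86 per group is reproduced.

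**Assumptions for missed influenza.** The documents give no attack rate. Take a fraction p of 1% to 5%, missed equally in both arms and all on one strain: 0.9 to 4.3 subjects of 86 per arm.

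**(a) Infection adds 3 log2 in both arms.** The difference in means is unchanged and the variance grows: SD = √(4 + 9p(1−p)). Overall power = 0.9475³ × power for the affected strain, with 0.9475³ = 0.8505.

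| p | SD | Power, affected strain | Overall power | Type I error |
|---|---|---|---|---|
| 0 | 2.000 | 94.7% | 80.6% | 5.0% |
| 1% | 2.022 | 94.4% | 80.2% | 5.0% |
| 3% | 2.064 | 93.6% | 79.6% | 5.0% |
| 5% | 2.104 | 92.8% | 78.9% | 5.0% |

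**(b) Extreme case: infected subjects have the same mean titer in both arms.** A true log2 difference of 1 is seen as 1 − p, so a true ratio of 2 is seen as 2^(1−p). SD is held at 2. The overall false-conclusion rate takes the other three strains at a true ratio of 1: per-strain type I error × 0.8505.

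| p | Ratio seen | Type I error, affected strain | Overall false conclusion |
|---|---|---|---|
| 0 | 2.00 | 5.0% | 4.3% |
| 1% | 1.99 | 5.3% | 4.5% |
| 3% | 1.96 | 6.1% | 5.2% |
| 5% | 1.93 | 6.9% | 5.9% |

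The last column reaches 5% only at about p = 2.4%.

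**What detection would cost.** A detected case leaves the set for all four strains. Within the 5% allowance, 86 per arm and 80.6% still hold. If a further 1% or 5% were lost, 85 or 81 per arm remain, and overall power is 0.9454⁴ = 79.9% or 0.9362⁴ = 76.8%. Both are below the 80.2% and 78.9% obtained by leaving the cases in under (a).

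**The texts side by side.** Section 9.2.3 says RSV will be assessed on the swabs; it does not say RSV alone. Swabs are taken for any respiratory symptoms. Section 11.1 names RT-PCR for influenza without requiring a study swab, so a result from the subject's own care would qualify. Both sections can hold at once.

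**The case for a change.** The best case for acting is that this rule governs the primary set, that the sponsor expected it to operate because Section 11.2 budgets for influenza, and that nothing described makes it operate systematically. An adverse event diagnosis without an influenza test behind it is incidental evidence. Blinding balances missed cases between arms, but balance does not make them neutral in a non-inferiority test, as (b) shows. The remedy could be short: either say that the swabs are also tested for influenza, or delete RT-PCR from the influenza rule.

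The textual observation stands: no influenza test is described, and detection as described would be patchy. The remedies are weaker. Deleting RT-PCR finds no infection, leaves the bias in (b) untouched, and could discard a positive RT-PCR result obtained outside the study, the strongest evidence available. Adding an assay brings a laboratory step of unstated cost, with results needed before the first analysis, because "at 28 days post-first dose, an immunogenicity analysis will be performed by an independent unblinded statistician" and this feeds the decision on repeat influenza immunization after Day 57. Swabs would still be taken only where feasible, so cases would still be missed. The benefit appears only under (b), which requires infection to remove all dependence on vaccine response and every missed case to fall on one strain.

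**Conclusion.** No change to the plan follows. The protocol leaves one test undescribed; it does not contradict itself. The exclusion can be applied as worded through external results, diagnoses on the adverse event page, serious adverse event reports, and the unscheduled evaluations allowed by Section 3.1. Which of these count can be settled in the SAP.

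The primary conclusion is little affected. Under a common rise, type I error does not move and overall power loses 0.4 to 1.7 percentage points (80.6% to 80.2% or 78.9%). Under the extreme mechanism, per-strain type I error is 5.3% at 1% missed and 6.9% at 5%. These figures rest on assumed infection rates, an assumed rise of 3 log2, a true ratio of 1 where power is quoted, and independent strains; the documents cannot settle the real size. The exposure window is also short: from Day 1 to a draw scheduled for Day 29 ± 3 days, with a possible delay of up to 10 days for illness.

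A sentence in Section 9.2.3 saying whether the swabs are also tested for influenza would help a reader if that section were being edited anyway. The sample size and the primary test do not depend on it.
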